5.1.1. Phase 1a Dose Escalation

Phase 1a of the study will target the following tumor types: triple negative breast cancer, pancreatic cancer, PD-1 refractory NSCLC, PD-1 refractory RCC, PD-1 refractory melanoma, metastatic castrate resistant prostate cancer (mCRPC) and ovarian cancer. In **Cohort A** in Phase 1a, escalating doses of single agent LY3475070 will be evaluated in at least 3 evaluable patients per dose level (i.e., DLA1-A4). The dose limiting toxicity (DLT) observation period will be 28 days. The first patient of each DL will be observed for 48 hours before additional patients are enrolled to that DL. The totality of safety data will be reviewed by the Lilly clinical research physician/clinical research scientist (CRP/CRS) and study investigators prior to escalating to a next DL. Intra-patient dose escalation is not allowed.

It is anticipated that a minimum of 4 DLs will be evaluated in Cohort A to determine the MTD of single agent LY3475070, or, in the absence of MTD, a recommended Phase 1b dose of single agent LY3475070. The final MTD will be the dose for which the estimated toxicity rate is the closest to the target toxicity rate of 30% and less than 35%. The recommended Phase 2 dose (RP2D) to be formally established in Phase 1b part of the study will be based upon the totality of safety, PK and pharmacodynamic data, and thus may be lower than the MTD or the recommended Phase 1b dose identified in the Phase 1a part of the study.

Once the DLA2 (300 mg QD) for single agent LY3475070 is determined safe and enrollment to DL3 has commenced, LY3475070 in combination with pembrolizumab will be evaluated in **Cohort B** in 3 to 6 patients starting at combination DL1 (150 mg QD LY3475070 and pembrolizumab) and escalated, independently from ongoing monotherapy dose escalation, to the recommended Phase 1b dose or MTD of LY3475070 single agent. The first patient of each DL will be observed for 48 hours before additional patients are enrolled to that DL. There will be no dose escalations for pembrolizumab, which will be given at 200 mg every 3 weeks (Q3W). The dose given in the dose escalation in Cohort B should not exceed the maximum dose shown to be safe in Cohort A.

Figure JZMA.5.1 illustrates the study design for Phase 1a dose escalation. Section 5.1.3 describes the details of the dose-escalation method used in this study.

Abbreviations: CDL = combination dose level; DL = dose level; mCRPC = metastatic castrate resistant prostate cancer; MTD = maximum tolerated dose; NSCLC = non-small cell lung cancer; PD-1 = programmed cell death-1; RCC = renal cell carcinoma; ref = refractory; RP2D = recommended phase 2 dose.

Figure JZMA.5.1. Illustration of study design for Phase 1a (dose escalation).

5.1.2. Phase 1b Dose Expansion

In Phase 1b of the study, the recommended phase 1 dose (RP1D) or MTD, as determined in the Phase 1a part, of LY3475070 alone or in combination with pembrolizumab will be evaluated in

3 distinct cohorts: Cohorts C, D, and E. The RP2D will be determined at the end of the Phase 1b part of the study based on the totality of data.

[figure not shown]
Cohort C will consist of patients that have been treated with and are refractory to PD-1/L1 inhibitor treatment with the following malignancies: NSCLC, RCC or melanoma. To be eligible, Cohort C will consist of patients with NSCLC, RCC, or melanoma that progressed on anti-PD1-L1 inhibitor therapy. Exception for prior anti- PD-1/L1 requirement will be given for NSCLC patients with EGFR activating mutations, as these patients do not respond to PD-1/L1 directed therapy, which may be due to high CD73 expression (Higgs et al. 2018; Streicher et al. 2017). In addition, patients must undergo a pretreatment biopsy and be positive for CD73 expression by central immunohistochemistry (IHC) testing.

Cohort D will consist of men with mCRPC; eligible patients must be PD-1/L1 inhibitor naïve.

To minimize physician/patient bias and to promote balanced patient characteristics between treatments, patients in Cohorts C and D will be randomized to either single agent LY3475070 or LY3475070 and pembrolizumab.

Cohort E will consist of patients with previously treated metastatic triple negative breast cancer (mTNBC) who will receive LY3475070 and pembrolizumab. Patients must have received at least one prior cytotoxic regimen. Prior anti PD-1/L1 treatment is not a requirement.

[Table JZMA.5.2](#) illustrates the study design for Phase 1b dose expansion.

[figure not shown]
Abbreviations: CD73 = cluster of differentiation 73; CDL = combination dose level; DL = dose level; mCRPC = metastatic castrate resistant prostate cancer; MTD = maximum tolerated dose; NSCLC = non-small cell lung cancer; PD-1 = programmed cell death-1; PD-1/L1 = programmed cell death-1/ligand 1; R = randomization; RCC = renal cell carcinoma; ref = refractory; RP1D = recommended phase 1 dose; TNBC = triple negative breast cancer.

^a If supported by data analysis, an additional 20 patients will be added

Figure JZMA.5.2. Illustration of study design for Phase 1b (dose expansion).

5.1.3. Dose-Escalation Methodology

Dose escalation of LY3475070 will be driven by the modified toxicity probability interval-2 (mTPI-2) method (Guo et al. 2017) where a pre-calculated decision table (Figure JZMA.5.3) will guide the dose recommendations until the MTD is determined (e.g., when all planned patients have been tested, or when no higher candidate DL can be tested). Dose escalation decision will also take into consideration available PK and pharmacodynamic data from previous DLs. Although mTPI-2 allows flexible number of patients in each dosing cohort, a minimum of 3 evaluable patients are required for the DLT evaluation at each DL. The first patient of each DL (in Phase 1a) will be observed for 48 hours before additional patients are enrolled to that DL. Inpatient dose escalation is not allowed.

$n = 20, p_T = 0.3, \epsilon_1 = 0.05, \epsilon_2 = 0.05$

E: Escalate to the next higher dose; **S**: Stay at the same dose; **D**: De-escalate to the previous lower dose; **DU**: De-escalate to the previous lower dose and the current dose will never be used again in the trial;

* If at the first dose level, users can choose to early-terminate the trial or not based on their own discretion.

Figure JZMA.5.3. Dose-finding algorithm of the mTPI-2 method showing number of patients treated and number of patients with DLTs.

This study is designed to identify a DL with a dose-limiting target toxicity rate of 30%. The mTPI-2 method considers an equivalence interval (EI) around the target toxicity rate. For this study, the EI is elicited to be (25%, 35%). Safety data, in particular DLTs, will be the primary criteria for the dose escalation. In addition, if available at the time of dose escalation decision, PK/pharmacodynamics results (for example, C_{max} , area under the concentration curve (AUC), pharmacodynamics results) will be used as secondary/supporting data for dose escalation. Intermediate and/or higher dose as well as alternative schedules of administration will be explored if deemed necessary after discussion between Lilly and investigators and taking into account patient safety and PK/pharmacodynamics data. If needed, additional patients may be enrolled to further assess PK/pharmacodynamics or tolerability.

In order to be DLT evaluable patients must have received 75% of LY3475070 scheduled dose within the 28-day DLT period unless patients have a DLT qualifying event. For patients treated with the combination treatment, patients must have received 75% of LY3475070 and a minimum of 1 pembrolizumab infusion within the 28-day DLT period.

5.2. Determination of Sample Size

The primary objective of this study is to assess the safety and tolerability of LY3475070, thereby identifying and confirming the RP2D of LY3475070, to be administered as monotherapy and in combination with pembrolizumab, in patients with advanced solid malignancies. The primary objective of the Phase 1b portion of this study also includes preliminary clinical activity evaluation by overall response rate (ORR) per RECIST v1.1, as monotherapy and in combination with pembrolizumab. The secondary objective is to evaluate PK and any observed evidence of clinical efficacy.

With a total sample size of N=20 or N=40, example point estimates of incidence rates and corresponding 2-sided 95% confidence intervals (CIs) are summarized in the table below. The values are provided as a reference for estimation rather than a basis of any decision criteria. The RP2D may be revised based on the safety data obtained in the expansion phase (Iasonos and O'Quigley 2013).

Table JZMA.5.2. Estimated Incidence Rate and 2-Sided 95% CI

N=20				N=40			
Number of Cases	Estimated Rate	95% CI ^a		Number of Cases	Estimated Rate	95% CI ^a	
		Lower Limit	Upper Limit			Lower Limit	Upper Limit
0	0.0	0.0	0.17	0	0.0	0.0	0.09
3	0.15	0.03	0.38	5	0.12	0.04	0.27
5	0.25	0.09	0.49	10	0.25	0.13	0.41
10	0.50	0.27	0.73	15	0.38	0.23	0.54
15	0.75	0.51	0.91	20	0.50	0.34	0.66

Abbreviations: CI = confidence interval; N = number of patients.

^a 95% Clopper-Pearson interval for binomial distribution.

6. A Priori Statistical Methods

6.1. General Considerations

Statistical analysis of this study will be the responsibility of Eli Lilly and Company. The interpretation of the study results will be the responsibility of the investigator with the Lilly CRP or CRS, pharmacokineticist, and statistician. The CRP or CRS and statistician will also be responsible for the appropriate conduct of an internal review for both the final study report and any study-related material to be authorized by Lilly for publication.

Sponsor standard tables, figures, and listings (TFLs) and supporting programs and software (e.g., TAFFY, BEACH) will be utilized for all analyses where a suitable standard exists. Data derivations in this SAP are defined, based upon current Sponsor reporting standards at the time of writing, and may be updated at the time of analysis in order to maintain accordance with the most current Sponsor standards at that time.

In general, continuous variables will be presented using the mean, standard deviation, coefficient of variation, median, minimum, maximum and number of patients with an observation (n). For categorical variables, the population size (N), the number of patients with events (n) and the percentage of patients with events are usually reported.

All confidence intervals (CIs) will be given at a 2-sided 95%, unless otherwise stated.

The data handling conventions and analysis populations are outlined in [Table JZMA.6.1](#).

Table JZMA.6.1. Data Handling Conventions and Analysis Populations

Term	Definition or Rule
Relative Study Day	If assessment is on or after date of first dose then (date of assessment) – (date of first study drug dose) +1
	If assessment precedes first dose of drug then (date of assessment) – (date of first study drug dose)
	There is no Study Day 0. Study Day 1 is the date of first dose and Study Day - 1 is the day before the first dose.
Cycle Day	If assessment is on or after date of first dose in cycle then (date of assessment) – (date of first study drug dose in cycle) +1
	There is no Cycle Day 0. Cycle Day 1 is the date of first dose in that cycle.
Baseline	For change from baseline analyses, baseline value is defined as the last reported measure on or before the first dose date (prior to the dose administration) unless, otherwise, specified.
Entered	All participants who sign informed consent
DLT evaluable	All patients enrolled in the dose escalation phase (Phase 1a) who either complete 28 days of follow-up and at least 75% of treatment doses or discontinue treatment prior to 28 days due to a DLT.
Randomized	(Phase 1b portion only). All patients in cohorts C and D who are randomized to a treatment regimen, regardless of whether they take any study drug.
PK evaluable	All enrolled patients who have at least 1 postbaseline evaluable PK sample.
Safety	All participants who take at least 1 dose of study treatment. Participants will be included in the treatment group corresponding to their initial dose of study treatment, even if it is not the treatment to which they were assigned. In the event of a treatment error, participants will be analyzed according to the treatment they actually received. “Enrolled” population also refers to the “Safety” population in this study.
Screen Failures	Patients who have signed informed consent, do not meet eligibility criteria and are not enrolled.

Abbreviations: DLT = dose-limiting toxicity; PK = pharmacokinetic(s).

Any change to the data analysis methods described in the protocol/SAP will require an amendment ONLY if it changes a principal feature of the protocol/SAP. Any other change to the data analysis methods described in the protocol/SAP, and the justification for making the change, will be described in the clinical study report. Additional exploratory analyses will be conducted as deemed appropriate.

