This study is designed to identify a DL with a dose-limiting target toxicity rate of 30%. The mTPI-2 method considers an equivalence interval (EI) around the target toxicity rate. For this study, the EI is elicited to be (25%, 35%), resulting in the rules below.

Safety data, in particular DLTs, will be the primary criteria for the dose escalation. In addition, if available at the time of dose escalation decision, PK/pharmacodynamics results (for example,  $C_{max}$ , area under the concentration curve (AUC), pharmacodynamics results) will be used as secondary/supporting data for dose escalation.

Intermediate and/or higher dose as well as alternative schedules of administration will be explored if deemed necessary after discussion between Lilly and investigators and taking into account patient safety and PK/pharmacodynamics data. If needed, additional patients may be enrolled to further assess PK/pharmacodynamics or tolerability.

In order to be DLT-evaluable, patients must have received 75% of LY3475070 scheduled dose within the 28-day DLT period unless patients have a DLT qualifying event. For patients treated with the combination treatment, patients must have received 75% of LY3475070 and a minimum of 1 pembrolizumab infusion within the 28-day DLT period.

In the dose escalation phase, once a given DL is cleared for DLT evaluation and is deemed safe, the dose cohort may be expanded to further investigate the safety, PK, pharmacodynamic, and clinical activity of LY3475070 and the combination with pembrolizumab. There will be up to 20 backfill patients enrolled across all dose levels in cohorts A and B combined in the phase 1a study. Any AEs reported by those backfilled patients that meet the DLT criteria as defined in Section 6.1.1.1 and occur in the DLT period are considered DLT-equivalent toxicities (Section 6.1.1.2). The cumulative safety data from the cohorts previously declared safe and the current dose cohort under evaluation will be continuously monitored. A Bayesian toxicity monitoring rule will be implemented for DLT-equivalent toxicities added from backfill patients (Section 9.2). These aggregate safety data will be included in defining the RP2D.

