### 6.1.1. Definition of DLT and DLT-ET

#### 6.1.1.1. DLT

A DLT is defined as any of the events listed in the table below, if both of the following criteria are met:

- the event occurs during the DLT observation period (28 days) in Phase 1a, and
- the event cannot, in the opinion of the investigator, be definitely attributed to primary disease or extraneous causes, such as accident.

Patients who experience a DLT in the DLT observation period will be discontinued from study treatment.

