**Other Hematologic or Nonhematologic Toxicity That May Be a DLT.**

- Toxicity deemed by the investigator and Lilly CRP to be dose limiting, such as:
  - toxicity that is possibly related to study treatment and requires discontinuation of the patient from the study at any time within the DLT observation period, or
  - persistent Grade >2 toxicities causing a delay of LY3475070 study treatment >14 days during the DLT observation period.

Abbreviations: AE = adverse event; ALT = alanine transaminase; AST = aspartate transaminase; CRP = clinical research physician; HCC = hepatocellular carcinoma; irAE = immune-related adverse event; IV = intravenous; ULN = upper limit of normal.

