	Grade 3	Withhold therapy until $\leq$ grade 1 then dose reduce LY3475070 (if rash worsens or does not improve in two weeks permanently discontinue) If Stevens–Johnson syndrome or toxic epidermal necrosis permanently discontinue patient	Initiate oral antibiotic (e.g., doxycycline). Initiate systemic corticosteroid (e.g., prednisone 0.5 mg/kg daily (maximum dose, 40 mg). Consider dermatology consultation.	Monitor for worsening signs and symptoms weekly until improvement to $\leq$ Grade 1. Resume LY treatment with 1 DL reduction. If rash does not improve or worsens after 2 weeks of treatment, discontinue LY permanently. If Stevens–Johnson syndrome or toxic epidermal necrolysis is suspected, discontinue permanently.
	Grade 4	Permanently discontinue	Initiate oral antibiotic (e.g., doxycycline). Initiate systemic corticosteroid (e.g., prednisone 0.5 mg/kg daily (maximum dose, 40 mg). Consider dermatology consultation.	
Diarrhea	Grade 1	Continue LY3475070 treatment. Start loperamide 4 mg initially, followed by 2 mg every 4 hours or after each stool.	Consider discontinue of lactose containing products	

Related AEs	Toxicity Grade or Conditions (CTCAE v5.0)	Action Taken to Therapy	AE Management	Monitor and Follow-up
	Grade 2	Continue LY3475070 treatment if Grade 2 diarrhea lasts <48 hours. Hold LY3475070 treatment if Grade 2 diarrhea lasts ≥48 hrs treatment until resolution to ≤ Grade 1.	Start loperamide 4 mg initially, followed by 2 mg every 4 hours or after each stool. Encourage oral hydration. If immune mediated colitis is suspected, consider GI consultation and biopsy.	
	Grade 3	Hold LY3475070 until resolution to Grade ≤ 1. Resume LY at 1 DL lower upon recovery.	If not already done, start loperamide 4 mg initially, followed by 2 mg every 4 hours or after each stool. Consider hospitalization for symptom and fluid management and GI consultation.	
	Grade 4	Permanently discontinue LY3475070 treatment	Consider hospitalization for symptom and fluid management, hydration and GI consultation.	
AST/ALT elevation or Increased bilirubin	Grade 1	Continue LY3475070 treatment	Review concomitant medications and alcohol use	

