### 9.3. Populations for Analyses

For purposes of analysis, the following populations are defined:

Population	Description
Entered	All participants who sign informed consent
DLT evaluable	All patients enrolled in the dose escalation phase (phase 1a) who either complete 3 weeks of follow-up and treatment or discontinue treatment prior to 3 weeks due to a DLT.
PK Evaluable	All enrolled patients who have at least 1 post baseline evaluable PK sample
Safety	All participants who take at least 1 dose of study treatment. Participants will be included in the treatment group corresponding to their initial dose of study treatment, even if it is not the treatment to which they were assigned. In the event of a treatment error, participants will be analyzed according to the treatment they actually received. “Enrolled” population also refers to the “Safety” population in this study.
Phase 1a	All patients assigned to a treatment cohort during the dose escalation portion of the study.
Phase 1b	All patients assigned to a treatment cohort during the dose expansion portion of the study.
CD73+	CD73+ by IHC

Abbreviations: DLT = dose-limiting toxicity; IHC = immuno-histochemistry; PK = pharmacokinetics.

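### The SAP's DLT-evaluable row has no route for a patient simply because a DLT occurred, so it conflicts with SAP 5.1.3 and protocol 4.1.1 and can lose a DLT in boundary cases

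*SAP*

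**What the plan says.** The SAP defines DLT evaluability twice.

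- **SAP 6.1, Table JZMA.6.1:** evaluable patients "complete 28 days of follow-up and at least 75% of treatment doses or discontinue treatment prior to 28 days due to a DLT". There are two routes. The first is completed follow-up with enough drug, whether or not a DLT occurred. The second is stopping early because of a DLT.
- **SAP 5.1.3:** patients "must have received 75% of LY3475070 scheduled dose within the 28-day DLT period unless patients have a DLT qualifying event". Having the event is enough, and nothing is said about stopping treatment. Protocol 4.1.1 has the same rule. Both sections also require at least one pembrolizumab infusion for combination patients, which the table omits.

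Protocol 9.3 has the two-route form of the SAP table, but with a 3-week period; its second route is to "discontinue treatment prior to 3 weeks due to a DLT". The DLT observation period is 28 days in protocol 4.1 and 6.1.1.1 and in SAP 5.1.1.

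Protocol 6.1.1.1 adds: "Patients who experience a DLT in the DLT observation period will be discontinued from study treatment". It sets no date by which this must happen.

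**The concern.** DLTs are a primary endpoint of Phase 1a and drive escalation. A set meant to hold everyone who is informative about DLTs should admit a patient because a DLT occurred. The table instead asks either for enough drug and follow-up, or for a particular disposition record: treatment stopped, before Day 28, because of the DLT. A DLT patient with neither is removed from numerator and denominator together.

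The first route does not protect patients whose toxicity led to a long interruption, and they are the ones most likely to be short of doses. Protocol 4.1.1 and SAP 5.1.3 include their waiver for such patients. Planned enrolment is 12 to 24 patients over four levels in Cohort A and 9 to 18 over three in Cohort B, or 3 to 6 per level in each, so one patient can decide whether the dose goes up.

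**Working it through.** **Step 1. Dose threshold.** With once-daily dosing over 28 days, 0.75 × 28 = 21 doses. A DLT patient who misses up to 28 − 21 = 7 doses and completes 28 days of follow-up is evaluable by the first route. With 20 doses (20/28 = 71%) the patient depends wholly on the second route.

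**Step 2. Who falls outside both routes.** The patient has a DLT, has fewer than 21 doses or incomplete follow-up, and has one of these:

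- a stop dated Day 28 or later;
- a stop coded to a reason other than the DLT;
- a hold not followed by discontinuation.

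Two boundary examples, counting days inclusively:

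- Protocol 6.1.1.1 lists, among events that may be judged dose limiting, persistent "toxicities causing a delay of LY3475070 study treatment >14 days during the DLT observation period". If the hold starts on Day 14, Days 14 to 28 are 15 days, so the criterion is first met on Day 28. Doses taken are 13/28 = 46%. A hold starting on Days 1 to 13 meets the criterion before Day 28; one starting after Day 14 cannot meet it within the window.
- Grade 3 fatigue lasting more than 7 days, with drug withheld from Day 21: Days 21 to 28 are 8 days, so the criterion is first met on Day 28. Doses taken are 20/28 = 71%.

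If the stop is dated by the decision, neither patient stopped before 28 days. If it is dated by last dose (Day 13 and Day 20), both did. The table does not say which date governs. Under SAP 5.1.3 both count either way.

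**Step 3. Reproduce the plan's mTPI-2 decisions.** Inputs from the documents are target 0.30 and equivalence interval 0.25 to 0.35. Assumed are a Beta(1,1) prior for mTPI-2, sub-intervals of width 0.10 outward from the equivalence interval, and DU when P(p > 0.30) > 0.95. With x DLTs in n patients the posterior is Beta(1 + x, 1 + n − x). The decision follows the interval with the largest unit probability mass, UPM = posterior probability ÷ interval width.

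This gives 1/3 Stay, 1/6 Escalate, 2/3 De-escalate and 5/7 DU (the worked examples in protocol Appendix 8) and 2/6 Stay (protocol 4.1.1). All five match.

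**Step 4. Remove one DLT patient (x and n each fall by 1).** For 2/6 and 1/5:

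| Interval | 2/6, Beta(3,5) | 1/5, Beta(2,5) |
|---|---|---|
| 0.15–0.25 | 0.1698/0.10 = 1.70 | 0.2425/0.10 = **2.43** |
| 0.25–0.35 | 0.2241/0.10 = **2.24** | 0.2149/0.10 = 2.15 |
| 0.35–0.45 | 0.2158/0.10 = 2.16 | 0.1555/0.10 = 1.56 |
| Decision | Stay | Escalate |

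Other changes:

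| All DLTs counted | One DLT patient dropped |
|---|---|
| 1/4 Stay | 0/3 Escalate |
| 2/4 De-escalate | 1/3 Stay |
| 2/7 Stay | 1/6 Escalate |
| 3/7 De-escalate | 2/6 Stay |
| 4/6 DU | 3/5 De-escalate |

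For n = 4 to 10 with at least one DLT there are 4 + 5 + … + 10 = 49 cells. The decision changes in 14, and all 14 become less conservative.

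**The case against.** Several points on the other side stand.

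- **The table does not demand discontinuation of every DLT patient.** A reader might infer that a DLT counts only if treatment stopped before Day 28, so that anyone held, resumed or stopped later drops out. The first route rules that out: 28 days of follow-up and 21 doses suffice.
- **Protocol 6.1.1.1 takes DLT patients off treatment**, so most would enter by the second route. It is quoted here from the current protocol; the SAP was written to amendment (a). The rule narrows the gap but does not close it, because it sets no deadline and the table does not say how a stop is dated.
- **Dating by last dose rescues both examples in the working.** SAP 6.9.1 measures duration of therapy by last dose date, so that reading is reasonable, but it is not stated for this row.
- **Hold-and-resume is not clear evidence of lost DLTs.** For Grade 3 diarrhoea, protocol 6.6.1 says to hold and then "Resume LY at 1 DL lower upon recovery"; protocol 6.6.2 withholds drug for Grade 3 colitis. A reader might infer that DLT patients will routinely be re-dosed and then excluded. Protocol 6.1.1.1 says they are discontinued, and Grade 3 diarrhoea is a DLT only if it lasts more than 48 hours despite optimal supportive care. The passages are in tension, but they do not establish routine re-dosing.
- **No section says the table governs the DLT count.** SAP 6.9 lists DLTs by dose level among summaries of all treated patients, and escalation is described in SAP 5.1.3, which carries the waiver. A reader might infer that the DLT rate is biased downward. The documents do not support that as a demonstrated result.

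The table still matters. SAP 5.1.3 requires at least 3 evaluable patients per level, and SAP 6.3 uses DLT evaluability in defining Phase 1a completion. Counts from one set and denominators from another could disagree.

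**Conclusion.** The point holds as a narrow correction. Table JZMA.6.1 contradicts SAP 5.1.3 and protocol 4.1.1 on who is DLT evaluable, and protocol 9.3 shares the defect with a different period. The patients at risk have a DLT, fewer than 21 of 28 doses or incomplete follow-up, and no recorded stop before Day 28 because of the DLT.

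How often this would happen cannot be derived from the documents. If it happened and the table were applied, one lost patient would leave the mTPI-2 decision unchanged (35 of the 49 cells) or make it less cautious (14 of 49). This rests on the prior, sub-intervals and DU cutoff assumed in the working, which reproduce every decision the documents state, and on the patient being removed from both numerator and denominator.

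**What to change.** Reword the DLT-evaluable row in SAP Table JZMA.6.1, and protocol 9.3 with it, to admit a Phase 1a patient who either:

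- completes 28 days of follow-up with at least 75% of scheduled LY3475070 doses and, in Cohort B, at least one pembrolizumab infusion; or
- has a DLT within the 28-day period, regardless of doses taken or discontinuation.

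This carries the sponsor's own waiver from SAP 5.1.3 and protocol 4.1.1 into the population definitions, and replaces 3 weeks with 28 days in protocol 9.3. Add a statement that this set is used for the DLT count at each dose level.

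The cost is one sentence in each document plus that statement. No patients or data are needed.

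Separately, the sponsor must reconcile protocol 6.1.1.1 with the tables in 6.6.1 and 6.6.2 on what happens to treatment after a DLT-level event. Which rule is right is not a matter for this review; the proposed wording counts the DLT under either.
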